Patients with COVID-19 will be propensity score matched to patients without a COVID-19 diagnosis (minimum n=500), who will similarly be invited to participate in the study following eligibility checking by their general practice. This will constitute control group 1. Propensity scores will be estimated for the likelihood of COVID-19 using logistic regression, including the following data obtained from CPRD Aurum: age, sex, socio-economic status, body mass index (BMI), smoking status, comorbidities and risk factors for COVID-19 identified by Public Health England. A second control group of at least 500 participants will be derived from those with COVID-19 who do not report long-term symptoms (i.e., do not have Long COVID).

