**Data-driven analysis to identify distinct Long COVID syndromes (Objective 4, part A)**

We will define distinct symptom clusters (syndromes) using linked data from CPRD and Atom5™ platforms. We will employ clustering algorithms that have been shown to work well in medical settings, with binary and mixed variables: (1) complete linkage hierarchical clustering; (2) probabilistic c-means cluster analysis; (3) density peaked clustering analysis. We will evaluate algorithm performance and the optimal number of clusters (e.g. by internal validation against a holdout dataset using metrics such as Gap statistic and silhouette index).

We will describe the epidemiology of patients within each Long COVID syndrome as well as health service use (primary care consultations, prescriptions, A&E attendances and hospital admissions) and mortality risk and compare these to both sets of matched control patients. We will identify whether Long COVID syndromes are

associated with particular population groups such as BAME groups, patients with long-term conditions, and other vulnerable population groups identified by Public Health England.

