## **6.2 Matched controls - Group 1 (minimum of 500 participants)**

### **6.2.1 Eligibility Criteria**

Propensity score-matched individuals without a diagnosis of COVID-19 (suspected or confirmed) in CPRD Aurum and without a positive SARS CoV-2 RT-PCR result in linked SGSS data and without a record of hospital admission within 28 days of the index date will comprise Control Group 1. For propensity score matching we will use covariates such as sociodemographic characteristics, lifestyle and metabolic profile measures and presence of comorbidities, especially those identified as risk factors for COVID-19.

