**Figure 2.0 Participant recruitment**

### **6.5.2 Matched controls**

Sampling from the CPRD Aurum database, we will generate a propensity score matched control population of 500 individuals without a positive SARS CoV-2 RT-PCR result (Control Group 1) and 500 individuals with COVID-19 without Long COVID (Control Group 2), to assess the additional burden of Long COVID symptoms beyond what is observed in the infected population. Propensity scores will be generated using data on sociodemographic factors, lifestyle and metabolic profile measures and comorbidities. Matching will be done using the nearest-neighbour algorithm without replacement, considering callipers of width equal to 0.1. The index date for matching will be 1st January 2020. The CPRD Aurum ID for the matched control patients within Control Group 1 will be provided to the CPRD IRSP. CPRD will inform participating GP practices of these patients by providing the corresponding EMIS codes and will ask them to check their suitability for recruitment. The list of suitable patients will then be recorded on IRSP with the generation of a unique Global ID. Researchers at the University of Birmingham will not have access to Patient Identifiable Data until they have consented to participate on Atom5™. Participating GP's will invite eligible patients to take part via invitation letters, text message or email which will contain a copy of the PIS and a unique on-boarding code. Patients willing to take part will be instructed to use the on-boarding code to register on the Atom5™ platform.

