PCL-2	X						
modified MRC Dyspnoea Scale	X						
COVID-19 core outcome measure for recovery	X						
SBQ-LC	X						

All participants will be advised where to seek additional support should completion of the PROs raise any concerns regarding their well-being. Proxy-completion will be permitted via the app or website, or via telephone if the participant is unable to complete the PRO and will be documented on the app or website, or via the clinical portal.

Participants will be sent push notification reminders each month to complete the questionnaires on the day completion is due, at 2 days and again at 6 days. Both research personnel and patients will be provided with training resources and telephone support to help minimise missing data. Aparito will provide up to a maximum of two training sessions to the site staff online. A training video will be made available for those that need training after those two sessions. Finally, the site staff will be made aware of the IT support procedures and how to contact Aparito as needed. Aparito will be responsible for providing first line support only to the clinical team via UoB during the duration of the project. Training leaflets outlining how to download and use the app will be provided to staff and patients.

The health service use (primary care consultations, prescriptions, A&E attendances and hospital admissions) and mortality of patients from each Long COVID syndrome will also be described using data from CPRD Aurum and linked data from Hospital Episode Statistics and Office for National Statistics mortality statistics (via CPRD). We aim to use the most up-to-date healthcare data available from CPRD available up to 12 months of follow-up from initial registration on Atom5™.

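### Health service use is compared with both control groups, but use before the pandemic is named neither as a matching covariate nor as a baseline

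*Protocol*

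**What the plan says.** Section 5.0, WP2 (Objective 4 part A) lists the outcomes for each syndrome as "health service use (primary care consultations, prescriptions, A&E attendances and hospital admissions"), together with deaths, and adds "and mortality risk and compare these to both sets of matched control patients". Section 8.1 says where the data come from and how far they run: the latest "healthcare data available from CPRD available up to 12 months of follow-up from initial registration" on the app.

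The matching covariates appear in three places.

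- Section 5.0, WP1 (Objective 1), for Control Group 1: "age, sex, socio-economic status, body mass index (BMI), smoking status, comorbidities and risk factors for COVID-19 identified by Public Health England".
- Section 6.5.2, for both control groups: "Propensity scores will be generated using data on sociodemographic factors, lifestyle and metabolic profile measures and comorbidities".
- Section 6.2.1, for Control Group 1, in open form: "we will use covariates such as sociodemographic characteristics, lifestyle and metabolic profile measures and presence of comorbidities".

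None of them names earlier service use. Section 6.5.2 sets the index date for matching at 1 January 2020. For Control Group 1, section 5.0 says "Patients with COVID-19 will be propensity score matched to patients without a COVID-19 diagnosis". Control Group 2 is matched to the Long COVID participants (section 6.3.1).

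**The concern.** How often a person consults is largely a stable habit, and it is only partly explained by age, deprivation, smoking and recorded illness. Two groups that match on those items can still have differed in service use before anyone was infected. Three features of this design make that plausible.

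- Long COVID and Control Group 2 are separated by what participants report (sections 6.1.1 and 6.3.1). The symptom questionnaire asks about the last 7 days (section 9.1), so long-standing symptoms can place someone in the Long COVID group.
- Control Group 1 excludes people whose primary care record carries a code for suspected COVID-19 (section 6.2.3). This tends to remove people who take symptoms to their GP.
- Control Group 1 is matched to all COVID-19 patients. Even the listed covariates need not balance against the Long COVID subset, and section 2.0 itself reports higher prevalence in women and older adults.

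At stake is the meaning of any excess in consultations, prescriptions, attendances or admissions. Without a measure of earlier use, the comparison cannot tell new demand from demand that was already there. Precision is also lost, because earlier use is likely to be among the best available predictors of later use.

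**Working it through.** The protocol gives no rate, effect size or power for this comparison, so there is no stated figure to reproduce. The check has two parts.

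**1. What the document fixes**

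- Outcome and comparators: fixed (section 5.0, WP2).
- End of the data window: fixed at up to 12 months after registration (section 8.1). No earlier period is named, and none is ruled out.
- Covariates for Control Group 1: a definite list in section 5.0, WP1; the same domains in section 6.5.2; examples only in section 6.2.1. Prior use is in none of them.
- Timing: Control Group 1 is drawn by propensity score from CPRD Aurum and sent to practices before invitation (section 6.5.2). Its covariate set is therefore a design choice that cannot be redone at source once invitations have gone out.
- Availability: Box 1 describes CPRD as longitudinal and linked. It also dates the start of UK SARS-CoV-2 testing to 24 February 2020, so the 12 months before 1 January 2020 precede it.

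**2. Illustration of what an unbalanced habit would do**

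From the document: 500 Long COVID participants and 500 controls (Study Summary, minimum sizes). Assumed: mean 5 contacts a year, gamma-Poisson counts with dispersion 1, a personal rate that stays the same in both years, no true Long COVID effect, two-sided 5% level, and a habitual rate ratio R left after matching.

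For follow-up counts alone, the expected estimate is R, and

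SE(log RR) = √[ (1/(5R) + 1)/n₁ + (1/5 + 1)/n₂ ].

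For R = 1.2 and 500 v 500: √[(1.1667 + 1.2)/500] = 0.0688. Then log(1.2)/0.0688 = 0.1823/0.0688 = 2.65, and the chance of a significant result is about Φ(2.65 − 1.96) = 0.755. For R = 1.1 and 1.3 the same formula gives 28% and 97%.

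Simulation (400 runs per cell, Poisson regression with robust errors), without and with adjustment for log prior-year count:

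| Groups | R | Unadjusted RR | Significant | Adjusted RR | Significant |
|---|---|---|---|---|---|
| 500 v 500 | 1.0 | 0.99 | 7% | 1.00 | 6% |
| 500 v 500 | 1.1 | 1.10 | 32% | 1.02 | 6% |
| 500 v 500 | 1.2 | 1.20 | 74% | 1.04 | 15% |
| 500 v 500 | 1.3 | 1.30 | 97% | 1.05 | 26% |
| 125 v 500 | 1.1 | 1.09 | 12% | 1.02 | 6% |
| 125 v 500 | 1.2 | 1.20 | 41% | 1.03 | 11% |
| 125 v 500 | 1.3 | 1.30 | 72% | 1.05 | 15% |

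The 125 assumes that 500 Long COVID participants split equally over four syndromes. The closed form for 125 v 500 at R = 1.2 gives SE 0.108 and 39%, in line with the simulated 41%.

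Two limits show in the table. Adjustment removes most of the difference but not all, because one year's count measures habit with error. Where matching has already balanced habit (R = 1.0), both analyses stay close to 5%.

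**Precision.** A second simulation (500 v 500, mean 6 contacts, frailty variance 0.8, year-to-year correlation about 0.62 to 0.79, all assumed) had no imbalance. Adjusting for prior use cut the SE of the log rate ratio from 0.061 to between 0.048 and 0.040. That is 1 − 0.048/0.061 = 21% to 1 − 0.040/0.061 = 34%.

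**The case against.** The strongest reply is that the protocol never says the comparison will use follow-up counts alone. Section 5.0 gives no model, and section 8.1 says how late the data run, not how early. Section 10 sets out no service-use analysis, so adjustment for earlier use could sit in an analysis plan that is not shown. This stands: a reader might infer a planned follow-up-only analysis, but that inference rests on silence. It does not dispose of the matching covariates, which the protocol does state and which have to be settled before Control Group 1 is invited.

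Second, matching on comorbidity, BMI, smoking, socio-economic status and COVID-19 risk factors removes part of any difference, and section 6.2.1 is an open list. This also stands. The part that remains is unknown, and in the illustration the imbalance that goes in comes out by construction.

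Third, some routes to imbalance do not separate the groups. Control Group 2 also tested positive and also accepted a GP invitation, and Control Group 1 is invited through GPs too. The case rests on symptom self-report, the exclusion of coded suspected cases and the matching target.

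Fourth, service use is a secondary, largely descriptive output. No objective in section 3.2 names it, and the additional burden mentioned in section 6.5.2 is of symptoms. This limits the weight of the point. Even so, a stated comparison with matched controls invites an excess to be attributed to Long COVID.

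**Conclusion.** The point holds as a design weakness that is cheap to repair, not as an error in a stated analysis. The protocol fixes a comparison of service use with both control groups, states matching covariates that leave out earlier use, and names no baseline period. Differences in habitual use can remain and could be read as Long COVID burden.

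The documents do not support the stronger claim that heavy users will be mistaken for Long COVID burden. They give no figure for the imbalance after matching, which could be near zero. The illustrative result (rate ratio 1.20, significant in 74% of runs at 500 v 500, against 1.04 and 15% after adjustment) depends on the assumed 20% imbalance, contact rate and dispersion. It also assumes that personal rates persist unchanged. Weaker persistence from 2019 to the follow-up year would make adjustment less effective.

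Nor does it follow that change from prior use should be the main analysis. That method assumes that the groups would have followed parallel trends through the pandemic. It is unstable for sparse events such as admissions, and it cannot be applied to deaths.

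**What to change.** 1. In section 5.0 (WP1, Objective 1) and section 6.5.2, add the consultation rate in the 12 months before 1 January 2020, from CPRD Aurum, to the propensity models for both control groups. Name it in section 6.2.1 as well.
2. In section 5.0 (WP2, Objective 4 part A) and section 8.1, state that each service-use count is compared with adjustment for the participant's own use of that service in the same prior year.
3. Change from prior use (a ratio of rate ratios) may serve as a sensitivity analysis for frequent outcomes such as consultations and prescriptions. It should not be primary and does not apply to mortality.

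The cost is protocol wording and a few variables from CPRD and its linked hospital data. Section 15.1 says the university holds a CPRD licence and already has large parts of the data. Participants without a full prior year of registration need a stated missing category or exclusion, and a few matches may be lost. The change to the Control Group 1 matching has to be made before its invitations go out; the adjustment can be added later.

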### **Comparison of observed syndromes (symptom clusters) with known post-viral syndromes (Objective 4, part B)**

We will undertake a rapid review describing post-viral syndromes. The data will be synthesised to describe the post-viral syndromes that resemble the Long COVID syndromes identified in our data-driven cluster analysis. We will build on a rapid scoping review that we have undertaken to inform this proposal, on how post-viral syndromes from previous pandemic coronaviruses map onto the currently described complications experienced by those with COVID-19.

### **Immunological phenotyping of Long COVID syndromes (Objective 5, part A)**

Long COVID is associated with both systemic and organ-specific sequelae, including changes in the central nervous system. These are reminiscent of autoimmune phenomena arising following infections. Often these are transient; however, in some individuals they persist and generate post-infectious autoimmune sequelae. To study this, we will invite patients to obtain bio samples (saliva and blood) for a minimum of 250 patients with Long COVID and 50 patients in each of the control groups. We will measure common autoantibody profiles and use both antibody and T cell screens to identify specific self-antigens associated with long COVID, which may allow the identification of potential immunotherapies.

The extended hyperinflammation and immune activation seen with COVID-19 is also likely to accelerate the ageing of the immune system, including the generation of pro-inflammatory, tissue damaging senescent T cells. We will assess this in a sample of each of the symptoms clusters in the Long COVID cohort, and both sets of matched control patients, to determine if there is a preponderance amongst one or more syndromes. Their presence will suggest the utility of interventions to reverse immune ageing such as use of rapamycin analogs.

We will also look for the presence of potential diagnostic biomarkers in saliva and blood, focussing on small non-coding RNAs in saliva (sncRNAs) and over 7000 serum proteins using a proteomics platform (SomaScan®) to define dysfunction of a range of body systems. The main sncRNAs of interest are micro RNAs (miRNAs). These are RNA molecules (20-25 nucleotides) that regulate gene expression post-transcriptionally by either repressing translation or inducing degradation of messenger RNA. They are conserved across species, and are particularly stable in an extracellular environment, making them excellent candidates for use as biologic indicators of different physiologic states. The human genome encodes over 2000 miRNAs. They are produced by a wide variety of cells in different organs and secreted into the blood and other bodily fluids where they can exert biological effects. They are believed to control the activity of 60% of all of our genes. MiRNAs have been shown to play a central role in many biological processes including: the cell cycle, cell metabolism, apoptosis, immune responses and cancer progression. Amongst other roles, sncRNAs have been demonstrated to be very accurate biomarkers of acute and chronic brain injury.

### **Digital phenotyping (Objective 5, Part B)**

Continuous data collected on physical parameters such as exertions (heart rate, intensity and movement) and sleep patterns via the wearable devices integrated to the digital phenotyping app (Atom5™), will be used to describe patients with distinct Long COVID syndromes and create their physiological profile providing an understanding of the physical activities patterns linked to sleep, heart rate and intensity of physical movement.

**Outputs and deliverables:** We will describe distinct Long COVID syndromes and how they map onto the post-viral syndromes from previous pandemic coronaviruses. We will describe the epidemiology of Long COVID syndromes and characterise their immune, inflammatory, proteomic and physiological profile, providing mechanistic understanding of each syndrome and identifying potential therapeutic targets for future evaluation.

**WP3: Review of potential therapies for Long COVID syndromes and co-production of a remotely delivered supportive intervention for individuals with Long COVID (Objectives 6 and 7)**

**Overview:** We will identify potential pharmacological and supportive (non-pharmacological) therapies for managing individuals with Long COVID based on evidence from other post-viral syndromes, in combination with the evidence generated from WP2. We will work with patient partners and clinicians to co-produce a supportive intervention providing targeted support for managing long COVID syndromes that can be delivered remotely via the Atom5™ platform.

**Identification of existing pharmacological and supportive therapies for known post-viral syndromes and their applicability to individuals with Long COVID syndromes (Objective 6)**

We will conduct a rapid review evaluating the management of post-viral syndromes. We will identify current pharmacological and supportive interventions targeted at ameliorating common symptoms associated with impaired quality of life in similar post-viral syndromes (see Annex) in addition to treatments currently being considered for the management of Long COVID. We will map therapies to each of the Long COVID syndromes identified in WP2 as a foundation for discussion with experts and stakeholders in a series of participatory workshops (see next section).

[figure not shown]
**Co-production of a supportive, remotely delivered intervention for people with Long COVID (Objective 7)**

We will apply person-centred design principles to co-produce a supportive, remotely delivered intervention with key stakeholders: patients and their family members, healthcare professionals, experts in relevant symptoms and corresponding interventions, regulators, and policymakers (NICE).

Co-production will be guided by the “building blocks of co-production” framework. A series of expert consensus workshops will be convened to make recommendations on: 1) supportive/pharmacological therapies to be used in each Long COVID syndrome; 2) therapies to be evaluated in a clinical trial; 3) therapies that should not be recommended, based on the cumulated evidence from the rapid systematic review and primary findings from WP2. The consensus workshop will follow the James Lind Alliance final priority setting method, based on Nominal Group Technique. In addition, decision making will be guided by the APEASE criteria. Particular consideration will be given to non-pharmacological therapies (e.g., physiotherapy, breathing techniques, sleep hygiene) that can be delivered digitally and at scale.

Intervention co-production workshops will then be held to determine which of the agreed interventions are suitable for or could be adapted for remote delivery.

**Outputs and deliverables:** A co-produced targeted intervention for Long COVID syndromes that can be delivered remotely on a digital platform.

## 6.0. Participant selection and Eligibility

### 6.1 Population-based representative cohort of individuals with COVID-19 (minimum 2000 participants)

#### 6.1.1 Eligibility Criteria

Non-hospitalised individuals with a positive RT-PCR test for SARS-CoV-2 in SGSS data linked to CPRD Aurum. Those from that cohort reporting symptoms associated with COVID-19 at least 12 weeks from the diagnosis will be defined as having Long COVID.

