### 3.2 Research Objectives

1. To establish a representative population-based cohort of non-hospitalised individuals with COVID-19 and prolonged symptoms ("Long COVID").
2. To develop and validate a new patient-reported outcome (PRO) measure of symptom burden in individuals with Long COVID.
3. To collect validated PROs including symptoms, quality of life and work capability data longitudinally from the representative cohort of individuals with Long COVID using the Aparito Atom5™ platform.
4. To identify distinct symptom clusters ("syndromes") in non-hospitalised individuals with Long COVID and compare these Long COVID syndromes to known post-viral syndromes.
5. To measure immunological, proteomic and miRNA biomarkers to determine the underlying pathogenesis associated with Long COVID syndromes. To measure physical parameters via a wearable device to determine the physical exertions (heart rate intensity and movement) and sleep patterns observed in Long COVID syndromes.
6. To make recommendations on pharmacological and supportive therapies that: i) should be implemented without need for further evaluation; ii) should be evaluated in a clinical trial, and iii) should not be recommended for treating long COVID based on the available evidence.
7. Co-produce a supportive, remotely delivered intervention for individuals with long COVID, to address the symptoms associated with each Long COVID syndrome.
8. To evaluate patient and public involvement in the study.

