#### **Establish a representative population-based cohort of individuals with Long COVID (Objective 1)**

A representative population-based cohort of non-hospitalised individuals with Long COVID will be established using primary care records in the Clinical Practice Research Datalink (CPRD) and recruitment through the Interventional Research Services Platform (IRSP). We will use linked data from the Second-Generation Surveillance PCR-confirmed COVID-19 registry to identify all confirmed COVID-19 patients in CPRD. Using linked Hospital Episode Statistics (HES) data we will identify and exclude hospitalised patients. Further details on each of the data sources is provided (Box 1).

All potential cases will be reported to the Clinical Practice Research Datalink's (CPRD) Interventional Research Services Platform (IRSP). This is a web-based research platform linked to CPRD's anonymised primary care database of coded clinical electronic health care data from approximately 1700 practices across the UK. The platform enables primary care staff to review pre-selected patient lists, confirm eligibility and invite patients to join a study. The selection criteria are applied within the CPRD IRSP, based on the predefined patient selection strategy. A delegated health professional at each practice can subsequently access the pseudonymised patient list, re-identify the patients, and review the clinical record to a set of screening questions. For patients that meet selection criteria, the primary care team will send out an invitation letter informing them about the study and containing key links and information required to enable enrolment onto the study.

Via IRSP, all potential cases will be presented to participating general practices to review their suitability for study recruitment. Those assessed as suitable for study recruitment will be sent an invitation letter to participate in the study. We aim to recruit a minimum of 2000 individuals with COVID-19. Individuals from underrepresented sociodemographic groups (e.g., Black and Minority Ethnic (BAME) and those from areas of high socioeconomic deprivation) will be oversampled. These individuals with COVID-19 (minimum n=2000) will be invited to report symptoms, quality of life and work capability through the Aparito Atom5™ digital platform. Data collected from this cohort of patients with COVID-19 will be used to identify a sub-cohort of patients with long-term symptoms of Long COVID (minimum n=500, aiming for n≥750).

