### **Second-Generation Surveillance System (SGSS)**

SGSS is the national laboratory reporting system used in England to capture routine laboratory data on infectious diseases and antimicrobial resistance. The SARS-CoV-2 testing started in UK laboratories on 24/02/2020, with the SGSS data reflecting testing (swab samples, PCR test method) offered to those in hospital and NHS key workers (i.e., Pillar 1). The linked SGSS data only contains positive tests results. The primary care data itself includes both positive and negative Pillar 2 PCR and other RNA detection COVID-19 test results and it is estimated that over 80% of all such tests undertaken in England are being matched to GP records.

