#### 6.1.2 Inclusion criteria

Non-hospitalised individuals aged 18 years and over with a SARS CoV-2 RT-PCR result in SGSS data linked to CPRD Aurum, and willing to provide informed consent and to undertake the protocol activities.

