#### 6.1.3 Exclusion criteria

Individuals without a positive SARS CoV-2 RT-PCR test result in CPRD Aurum.

Individuals with a hospital admission within 28 days of a positive SARS CoV-2 RT-PCR result in CPRD AURUM.

Individuals aged under 18 years.

Individuals unable/unwilling to provide informed consent.

Individuals unable/unwilling to undertake the protocol activities.

Individuals deemed appropriate for exclusion by their GP (e.g., on a palliative care register).

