## **6.5 Participant identification and recruitment**

6.5.1 Population-based representative cohort of individuals with Long COVID

[figure not shown]
Researchers from The University of Birmingham will use linked data from the Second-Generation Surveillance (SGSS) data that contain SARS CoV-2 positive RT-PCR results to identify patients with confirmed COVID-19 in CPRD Aurum. Using linked Hospital Episode Statistics (HES), the research team will identify and exclude patients who have been hospitalised within 28 days of a positive SARS CoV-2 RT-PCR result or COVID-19 diagnosis).

The list of CPRD Aurum IDs of patients identified as potentially eligible (as above) by the research team will be provided to CPRD. The list of suitable patients will then be uploaded onto the CPRD Interventional Research Services Platform (IRSP). IRSP will generate a unique “username” (Global ID) for each patient on that list, which will be shared with Aparito to assist with verifying participants registering on the Atom5™ app. CPRD will inform participating GP practices that the patient list is available for them to review on by logging onto IRSP. GPs will identify the patients using the corresponding EMIS ID and screen them for their suitability for this study. Researchers at the University of Birmingham will not have access to Patient Identifiable Data until they have consented to participate on Atom5™.

GPs will then invite eligible patients to take part via invitation letters, text message or email which will contain the patient information sheet (PIS) and a username and unique one time password for the Aparito Atom5™ platform. Patients will then log on Atom5™ and provide e-consent (which includes confirming their eligibility) and log data on their symptoms and patient-reported outcomes (PROs). From this data we will identify individuals with prolonged symptoms (>12 weeks) associated with COVID-19, which will form the long COVID cohort.

Participants will be provided a £10 Amazon voucher code via Atom5™ upon completing the baseline questionnaires and a further £10 Amazon voucher upon completing the final study questionnaires at 12 months of follow-up.

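### Cases are drawn only from linked SGSS positives, which the protocol itself describes as Pillar 1 testing, so community-tested (Pillar 2) cases have no route into a cohort meant to be representative

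*Protocol*

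**What the plan says.** Objective 1 in section 3.2 is "To establish a representative population-based cohort of non-hospitalised individuals with COVID-19 and prolonged symptoms".

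Five places set out how cases are found, and all name SGSS:

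- Section 5.0, WP1: "We will use linked data from the Second-Generation Surveillance PCR-confirmed COVID-19 registry to identify all confirmed COVID-19 patients in CPRD". Section 14.2 says the same of CPRD Aurum.
- Section 6.1.1: "Non-hospitalised individuals with a positive RT-PCR test for SARS-CoV-2 in SGSS data linked to CPRD Aurum".
- Section 6.1.2: "Non-hospitalised individuals aged 18 years and over with a SARS CoV-2 RT-PCR result in SGSS data linked to CPRD Aurum".
- Section 6.5.1: the research team "will use linked data from the Second-Generation Surveillance (SGSS) data that contain SARS CoV-2 positive RT-PCR results to identify patients with confirmed COVID-19".

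Box 1 describes what the linked SGSS data cover. They hold positives only and reflect swab PCR testing "offered to those in hospital and NHS key workers (i.e., Pillar 1". Box 1 then turns to the primary care data, which it says contain Pillar 2 PCR results, positive and negative, and adds that "it is estimated that over 80% of all such tests undertaken in England are being matched to GP records".

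Section 6.1.3 excludes "Individuals without a positive SARS CoV-2 RT-PCR test result in CPRD Aurum". It also excludes anyone admitted to hospital within 28 days of a positive test. Section 15.1 recognises the risk of a non-representative cohort and answers it by pointing to recruitment through CPRD.

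**The concern.** The study is about people who were not hospitalised, and many such people would be expected to have been tested in the community. On the protocol's own account of its data, the source chosen for case finding does not hold community tests, while the source that does hold them is not used. The selection happens before any GP or patient is approached, because the list sent to CPRD is built from this rule (section 6.5.1).

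If the rule is applied as written, later results inherit the restricted frame: Long COVID frequency, work capability, the symptom clusters, and the SBQ-LC cut-offs that section 10.2 intends for use in the general population. Occupation is not named among the propensity-score covariates in section 5.0, so an occupational difference between cases and Control Group 1 would not be matched out by design.

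**Working it through.** The protocol gives no figure on this point to reproduce. The check is a comparison of passages, followed by a sensitivity range for the one quantity a reader will want.

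**Step 1. Who can be listed as a case?** Sections 5.0, 6.1.1, 6.1.2, 6.5.1 and 14.2 require an SGSS positive. Box 1 gives two groups in SGSS: people in hospital and NHS key workers.

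**Step 2. Who is removed?** Sections 6.1.3 and 6.5.1 remove those admitted within 28 days. What remains is NHS key workers who were not admitted, plus people tested in hospital who were not admitted.

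**Step 3. Where do Pillar 2 positives go?** By Box 1 they sit in the primary care data. With no SGSS positive they fail 6.1.1 and 6.1.2, so they are not cases. Those with a COVID-19 diagnosis in CPRD Aurum are also barred from Control Group 1 by 6.2.2 and 6.2.3. They fall out of the study altogether.

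**Step 4. Is the source stated consistently?** No. Inclusion (6.1.1, 6.1.2) names SGSS linked to Aurum; exclusion (6.1.3) names Aurum. An exclusion can only remove people, so 6.1.3 does not bring Pillar 2 positives in.

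**Step 5. What share of the remaining cases would be key workers?** The protocol does not say. Assume:

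- k = share of SGSS positives who are NHS key workers (assumption), all treated as not admitted
- q = share of the other, hospital-tested positives with no admission within 28 days (assumption)

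Key-worker share = k / (k + (1 − k)q).

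- k = 0.1, q = 0: 0.1/0.1 = 100%
- k = 0.1, q = 0.10: 0.1/(0.1 + 0.09) = 53%
- k = 0.1, q = 0.25: 0.1/(0.1 + 0.225) = 31%
- k = 0.1, q = 0.50: 0.1/(0.1 + 0.45) = 18%
- k = 0.3, q = 0.10: 0.3/(0.3 + 0.07) = 81%
- k = 0.3, q = 0.50: 0.3/(0.3 + 0.35) = 46%
- k = 0.5, q = 0.50: 0.5/(0.5 + 0.25) = 67%

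The share passes one half when k > (1 − k)q, that is when q < k/(1 − k). The threshold is 0.11 for k = 0.1, 0.25 for k = 0.2 and 0.43 for k = 0.3. At k = 0.5 any q below 1 suffices.

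The omission in step 3 does not depend on k or q.

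**The case against.** The best reply is that the fault may lie in Box 1 and not in the eligibility rule. Its Pillar 1 description follows a remark on when testing began and could be read as an account of the early period. The same box calls SGSS the national laboratory system, and sections 5.0 and 14.2 treat it as complete. This stands in part: the document cannot settle what the linked extract contained at recruitment. But Box 1 contrasts SGSS with the primary care data in the present tense, and either way one of the texts is wrong.

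A second reply is that the source is not purely SGSS. The study summary speaks of GP records, section 6.1.3 of CPRD Aurum, and sections 6.4.1 and 6.5.1 mention a COVID-19 diagnosis. None of these adds a route in. The summary is general, 6.1.3 is an exclusion, 6.4.1 concerns people already in the study, and the mention in 6.5.1 only dates the admission exclusion.

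A third reply is that under-represented groups are oversampled (sections 5.0 and 14.2) and occupation is recorded at baseline (section 8.1 and Table 1.0). Oversampling works inside the restricted list. Recording occupation would show an imbalance but cannot recover people who were never invited.

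Three stronger readings are tempting, and the documents do not support them:

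- A reader might infer that the cohort would be mostly health workers. No split is given, and people tested in hospital but not admitted stay eligible.
- A reader might take the over-80% figure as the share of community cases that could be recruited. It is the matching of tests, positive and negative, to GP records in England. Recruitment runs only through participating CPRD practices.
- A reader might read 6.1.2 and 6.1.3 together as demanding a record in both sources. Loose wording for linked data is the likelier explanation.

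**Conclusion.** The point holds as a conflict within the protocol that has a direct consequence for selection. Followed as written, the rule gives no entry to anyone whose only positive result was a Pillar 2 test. That is incompatible with identifying every confirmed case in CPRD and with the representative cohort of Objective 1. Recruiting through CPRD does not cure it, because the filter is applied within CPRD.

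This rests on one assumption: that Box 1 describes the linked SGSS extract correctly. If it does not, the cohort may be sound and the error is in the description. The direction of the selection is clear on the stated facts, but its size is not. The key-worker share ranges from 18% to 100% over the assumed values above. Nor do the documents allow an estimate of how many Pillar 2 cases could be recruited.

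**What to change.** First establish what the linked SGSS extract contains.

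- **If it is Pillar 1 only:** in sections 5.0 (WP1), 6.1.1, 6.1.2, 6.5.1 and 14.2, define a case as a positive SARS-CoV-2 RT-PCR result in linked SGSS **or** in the CPRD Aurum record. Reword 6.1.3 to exclude people with no positive RT-PCR result in either source. Apply the existing 28-day admission exclusion to a positive from either source. Record which source identified each case and report it as a descriptor of the cohort.
- **If it already includes Pillar 2:** correct Box 1, and make 6.1.3 name the same source as 6.1.1 and 6.1.2.

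The cost is a change to the selection code and the wording, handled as an amendment under section 16.0 if it counts as substantial. Section 15.1 says large parts of the necessary data are already held, but does not say that Pillar 2 results are among them, so this needs checking. Some GP-coded results may be miscoded. GP screening of every listed patient (sections 5.0 and 6.5.1) reduces that risk without removing it. The change should be made before the list goes to CPRD, since people left off it are never invited.
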